study addressed the use of VR for patients suffering from complicated grief (grief that does not resolve over time) (Quero *et al.* , 2019) . A CBT protocol was followed using the traditional face-to-face or VR method, and the results were compared at the end of treatment, and at 6 and 12 months of follow-up. Although both methods led to significant improvements over time, the VR group was superior in clinically significant long-term change (Quero *et al.* , 2019) . The VR system used was EMMA's World, a system that has already been used in the treatment of post-traumatic stress and adjustment disorders (Guillén *et al.* , 2018) . The purpose of this system is to help process emotions associated with stressful events using 3D objects, sounds, music, and elements of personal meaning to the user. This system is also currently being used to provide psychological support after pregnancy loss, but at this time, only the protocol has been published (Corno *et al.* , 2020) . Currently, there are no published results on the use of VR systems explicitly targeted for gestational loss.

AViR Project

The AViR project is a project funded by FCT - Foundation for Science and Technology (EXPL/CCI-INF/0298/2021) that aims to fill this gap in the literature by proposing the use of a multi-scenario VR prototype that uses the adaptability of VR and traditional psychological support protocols to provide an adaptable intervention and personalized specifically oriented to grief after an early gestational loss. This prototype encompasses different virtual scenarios to address various aspects of the grief management process. All contents are defined with the collaboration of health professionals with experience in psychological support after gestational loss. The virtual scenarios are implemented in a VR display to increase the level of immersion and presence (Butussi & Chitaro, 2018), allowing the participant to be in a safe space where their emotions can be shared freely.

The present research study proposal aims to evaluate the feasibility of the proposed approach by testing the prototype system in a controlled pilot study with 20 women who suffered an early gestational loss in the last six months. We hypothesize that using the proposed VR paradigm will result in a significant reduction in symptoms

of grief, depression, anxiety, and post-traumatic stress, and that this reduction will be significantly superior when compared to the control group.

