The study we propose is very innovative regarding the target population and the use of VR, specifically designed to address gestational loss. In addition, it opens a new avenue of research on a topic that is still silenced and considered taboo in our society. Thus, this interdisciplinary research has an expected scientific, technological, and social impact, namely: 1) contributes to a better understanding of the process of psychological recovery after an early gestational loss; 2) contributes to the advancement of technologies aimed at psychological support; 3) has the potential to accelerate the resolution of grief by bringing emotional and psychological support to women who do not have access to other means of support; and 4) contributes to reducing the economic burden on health care by providing tools to improve the well-being of patients.

GOALS

This study has two main objectives:

- 1) Evaluate the impact of the proposed VR paradigm in women who suffered a gestational loss in the first 20 weeks of gestation, compared to a control group that follows the usual follow-up;
- 2) Evaluate the usability, user experience, and acceptance of the proposed approach.

METHODOLOGY

Sample and recruitment

The target population of this pilot study are women who have suffered involuntary pregnancy loss in the first 20 weeks of gestation. The recruitment of participants will be led by [name], in collaboration with the Obstetrics and Gynecology Service of SESARAM. We intend to recruit a sample of 20 participants who will later be divided into two groups, an intervention group using VR and a control group that will have access to standard monitoring.

Inclusion and exclusion criteria

Considering the objective and target population of the AViR project, the sample will be composed of women who have experienced early gestational loss, meeting the following **inclusion criteria**:

1. Have experienced an involuntary gestational loss in the first 20 weeks of pregnancy, in the last six months;
2. Be at least 18 years of age.

As **exclusion criteria**, we consider the following factors:

1. Have a diagnosis of mental disorder;
2. Be performing psychological intervention;
3. Being pregnant;
4. Having some visual deficit that may interfere with the normal performance of VR tasks.

[figure not shown]
Study design

To test the research hypothesis, the proposed study follows an experimental design, namely, a randomized controlled study with two independent

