conditions/groups (VR and Control). Participants who meet the inclusion criteria will be randomly allocated to one of the two groups described.

Data collection procedure

The pilot study will encompass a 4-week intervention and two evaluation moments: pre-intervention (baseline) and post-intervention, in which both groups, VR and Control, will participate. The VR group will have an intervention program lasting four weeks, with three weekly sessions of 45-60 minutes, using the developed prototype.

The VR prototype consists of VR glasses (Oculus Quest 2) where participants will experience different therapeutic modules, the contents of which were developed in collaboration with health professionals with experience in psychological support after pregnancy loss. The four modules cover: 1) **Psychoeducation**, to provide information about the grieving process, its phases, emotional and behavioral manifestations typical of this period; 2) **Validation of loss**, to recognize the loss and allow the performance of farewell and remembrance rituals; 3) Social sharing, to create a safe and judgment-free environment, conducive to sharing the experience

with others; and 4) **Adaptation to loss**, with a narrative that highlights the importance of physical well-being, social contact and the surrounding environment as fundamental elements for a healthy lifestyle. The intervention sessions with VR will be held by the master's student and graduate in Psychology, [name], who will decide which modules to apply in each session depending on each participant's response. The control group will do the standard follow-up, normally provided by SESARAM to this specific population. After the post-intervention evaluation, the control group will be given the possibility to use the VR system for four weeks, as in the case of the VR group.

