The pre- and post-intervention evaluation of both groups includes a set of instruments that aim to assess symptoms of grief, depressive and anxious, and post-traumatic stress. The evaluation of usability and user experience will be carried out only by the VR group after the intervention. All evaluations will be carried out by [name]. All participants will be duly informed of the objectives and procedures of the study, and will sign the participant information document and informed consent. The data collection sessions will take place in the spaces designated for this purpose in LifeTech Madeira (<https://lifetech.web.uma.pt>), according to the protocol signed by the University of Madeira and the Regional Secretariat of Health.

Data collection tools

To infer the possible effects of the intervention, all participants will respond to the following instruments validated for the Portuguese population, pre- and post-intervention:

- **Perinatal mourning:** *Perinatal Grief Scale (PGS)*, a version adapted for the Portuguese population (Rocha, 2004).
- **Post-Traumatic Stress:** *Post-traumatic Stress Disorder Checklist (PCL-5)* (DSM-5 (Diagnostic and Statistical Manual of Mental Disorders, 5th edition), Portuguese adaptation (Carvalho *et al.*, 2020) .

- **Depressive and Anxious Symptomatology:** *Hospital Anxiety and Depression Scale* (HADS), version adapted for the Portuguese population (Pais-Ribeiro *et al.*, 2007).

To assess the **usability and user experience** regarding the VR prototype, after the intervention, the participants allocated to the intervention group will complete questionnaires for the corresponding objectives, namely:

- **Usability:** *System Usability Scale* (SUS) (Brooke, 1996).
- **Presence:** *Sense of Presence Inventory* (ITC), adapted for the Portuguese population (Vasconcelos-Raposo *et al.*, 2019).
- **User experience:** a questionnaire with open questions on different aspects related to the experience of using the VR system.

In addition to the instruments mentioned, a **participant form** with relevant socio-demographic and clinical information will also be completed. All the instruments referred to are attached to this document.

Data processing and analysis

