The results of this study will be explicitly presented in tables and graphs. In terms of data description, categorical variables will be presented as absolute values or percentages, and quantitative variables will be presented through means, medians, standard deviations and quartiles. Regarding the statistical analysis tests, the chi-square test will be used to compare independent categorical variables; the Student's t-test to compare parametric variables; the Wilcoxon test to compare intra-subject nonparametric variables; and the Mann-Whitney test to compare nonparametric inter-subject variables. Correlations between variables will be performed using Pearson's coefficient for parametric variables and Spearman's coefficient for nonparametric variables. For all statistical comparisons, a significance level of 5% ($p < .05$) will be established. The data will be analyzed through the computer program SPSS 24.0 (IBM, NY, USA).

Dissemination of results

Considering the proposed project and the innovation of the paradigm and the interdisciplinary nature of this work, we aim to produce scientific publications in conferences and journals in the areas of Gynecology and Obstetrics, Psychology, Informatics applied to health, and/or human-computer communication. We also intend to disseminate the results obtained at regional and national level, specifically in health institutions. The goal will be to inform end-users and health professionals of the benefits that a system such as the one proposed can have on the population that has experienced an early pregnancy loss. Dissemination activities will also play an important role in raising awareness of this issue in society in general, thus contributing to increased psychological support interventions.

ETHICS

General considerations

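### The hypothesis compares symptom reduction between arms, but the only between-arm tests named ignore baseline and the compared score is not fixed; ANCOVA on data already collected would be more precise

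*Protocol*

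**What the plan says.** - **Hypothesis** (Protocol, AViR Project): symptoms will fall with VR, and "that this reduction will be significantly superior when compared to the control group". The second part is a between-arm comparison.
- **Design and size** (Protocol, Study design; Sample and recruitment): a randomised study with two independent groups. "We intend to recruit a sample of 20 participants who will later be divided into two groups". The allocation ratio is not stated.
- **Measurements** (Protocol, Data collection procedure; Data collection tools): there are two evaluation times, "pre-intervention (baseline) and post-intervention, in which both groups, VR and Control, will participate". PGS, PCL-5 and HADS are completed at both, so a baseline score exists for each scale in each arm.
- **Analysis** (Protocol, Data processing and analysis): for quantitative outcomes the list is "the Student's t-test to compare parametric variables", Wilcoxon for within-subject comparisons, and "the Mann-Whitney test to compare nonparametric inter-subject variables". Chi-square tests and Pearson or Spearman correlations complete it, all at the 5% level, in SPSS 24.0. The list has no ANCOVA, regression, mixed model or group-by-time term, and it does not say which score enters the between-arm test.

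**The concern.** The section commits to a list of tests, and every between-arm member of that list is unadjusted. That has two consequences.

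The first is lost precision. With about 10 women per arm there is little to spare. A comparison of post scores discards the baseline. A comparison of changes subtracts the whole baseline, which adds noise when the two measurements are only weakly correlated. Which of the two is better depends on that correlation, which the protocol does not give.

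The second is an open choice. A t-test on post scores and a t-test on changes both fit the text, and they can reach different verdicts on the same data. If the choice is made after the results are seen, the 5% level no longer holds.

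**Working it through.** **Inputs from the protocol.** Total N = 20; significance level 5%; each scale measured at baseline and post-intervention in both arms. The protocol gives no power, effect size, SD or correlation, so N = 20 has no derivation to reproduce.

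**Assumptions.** Allocation 10:10, normal scores, equal SD at both times (set to 1), two-sided testing, no dropout, pre-post correlation r from 0.3 to 0.8, true between-arm difference 1.0 SD.

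**Formulas.** With b = sqrt(1/n1 + 1/n2) = sqrt(1/10 + 1/10) = 0.447, the standard errors in SD units are:

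- post score: b, with 18 df
- change score: b × sqrt(2(1 − r)), with 18 df
- ANCOVA: b × sqrt((1 − r²)(1 + 1/(N − 4))), with 17 df. The factor 1 + 1/16 = 1.0625 is the expected cost of chance baseline imbalance at N = 20.

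Example at r = 0.5. Change score: 0.447 × sqrt(1.0) = 0.447. ANCOVA: 0.447 × sqrt(0.75 × 1.0625) = 0.447 × sqrt(0.797) = 0.399.

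**Results from the noncentral t distribution.** Cells are post score / change score / ANCOVA.

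| r | SE | Power at 1.0 SD | Effect detectable with 80% power (SD) |
|---|---|---|---|
| 0.3 | 0.447 / 0.529 / 0.440 | 56 / 43 / 57% | 1.32 / 1.57 / 1.31 |
| 0.5 | 0.447 / 0.447 / 0.399 | 56 / 56 / 66% | 1.32 / 1.32 / 1.19 |
| 0.6 | 0.447 / 0.400 / 0.369 | 56 / 66 / 72% | 1.32 / 1.19 / 1.10 |
| 0.7 | 0.447 / 0.346 / 0.329 | 56 / 78 / 82% | 1.32 / 1.03 / 0.98 |
| 0.8 | 0.447 / 0.283 / 0.277 | 56 / 92 / 93% | 1.32 / 0.84 / 0.82 |

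Simulation with 40,000 trials per r gave ANCOVA power of 57.8 / 65.8 / 72.8 / 81.8 / 92.8%, in agreement with the table. With 8:12 allocation and r = 0.5, power is about 55% for post or change scores and 64% for ANCOVA.

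**Where ANCOVA stops helping.** Its variance is below that of the post score when (1 − r²) × 17/16 < 1, that is r > sqrt(1/17) = 0.24. It is below that of the change score when (1 + r) × 17/16 < 2, that is r < 32/17 − 1 = 0.88. At r = 0 its power is 53% against 56% for the post score.

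**The unfixed score.** These figures come from 20,000 simulated trials per r.

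- With a true 1.0 SD difference, post-score and change-score t-tests disagree on p < 0.05 in 32 / 34 / 36 / 38 / 41% of trials at r = 0.3 / 0.5 / 0.6 / 0.7 / 0.8.
- With no difference, each t-test alone rejects in 4.7 to 5.2% of trials and ANCOVA in 4.9 to 5.2%. Taking the smaller of the post-score and change-score p-values rejects in 8.7 to 9.4%.
- Taking the smaller p-value of the t-test and Mann-Whitney on post scores gives only 5.2 to 5.4% (4,000 trials), so that choice matters little.

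**The case against.** The strongest reply is that nothing in the section is invalid. An independent t-test or Mann-Whitney test on changes fits the list, answers the hypothesis and holds its type I error. Naming the score and covariates is commonly left to a statistical analysis plan. The hypothesis speaks of reduction, which points towards change scores, and the 9% arises only if someone reports the better of two results, which the protocol nowhere proposes.

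The size of the gain can also be questioned:

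- It depends on an unknown r. Against change scores it is 82 − 78 = 4 points at r = 0.7 and about 1 at r = 0.8. Below about r = 0.24 ANCOVA is slightly worse than the post score.
- Disagreement between tests is weak evidence in itself, since ANCOVA also disagrees with each t-test in part of the trials.
- The figures assume normal scores. Diagnosed mental disorder is an exclusion, so skewed scores are plausible. In an illustrative right-skewed simulation (gamma, shape 0.8), Mann-Whitney on changes matched ANCOVA at r = 0.7 (80% against 81%) and at r = 0.8 (90% each), although ANCOVA led at r = 0.5 (70% against 64%).

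Much of this stands as a limit on size. It does not remove the point. The protocol does not leave the method open: it lists the tests, and an analysis plan that followed the list would have no baseline-adjusted comparison. If change is the intended score, that is the weaker choice at r below 0.5 (43% against 56% for post scores at r = 0.3). ANCOVA matches or beats both without r having to be guessed, except at low or very high correlation.

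**Conclusion.** The concern holds and should be fixed. The unadjusted tests are valid but inefficient for the stated hypothesis. Under the assumptions above (10 per arm, normal scores, equal SDs, two-sided 5%), ANCOVA at r = 0.5 raises power for a 1.0 SD effect from 56% to 66% and lowers the effect detectable with 80% power from 1.32 to 1.19 SD. Its variance is 0.797 of that of either unadjusted comparison, roughly what 20/0.797 = 25 women would give without adjustment. The gain is negligible over post scores at r = 0.3 and small over change scores at r = 0.8. The worst loss is about 3 points, against the post score at r = 0.

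Leaving the score unfixed is the secondary point: it permits a type I error of about 9% if the choice is made on the results. Neither point makes this a well-powered trial. Even with adjustment, 20 women can reliably show only large effects.

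**What to change.** In Data processing and analysis, state that the between-arm analysis of each scale (PGS, PCL-5, HADS anxiety, HADS depression) is one pre-specified ANCOVA of the post-intervention score on arm with that scale's baseline score as covariate, reported as an adjusted mean difference with 95% confidence interval. Name a permutation or rank-based version as a sensitivity analysis in place of data-driven switching between tests. Say also that the within-arm tests are descriptive and do not support the claim of superiority over control; the ANCOVA recommendation does not depend on this last sentence.

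The cost is a short amendment to the text. It needs no new data or visits and runs in the SPSS version already named. It uses one degree of freedom and, at N = 20, about 6% expected variance inflation, already counted in the figures above. It does not deal with testing four scores at 5% each, which is a separate matter.

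### The four-domain superiority hypothesis has no lead outcome and no success rule, so the same results could be read as supporting it or not

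*Protocol*

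**What the plan says.** The hypothesis closes the section on the AViR project. It has two parts: VR will significantly lower the burden "of grief, depression, anxiety, and post-traumatic stress, and that this reduction will be significantly superior when compared to the control group". The same paragraph says that the proposal "aims to evaluate the feasibility of the proposed approach by testing the prototype system in a controlled pilot study with 20 women".

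Objective 1, under Goals, is to "Evaluate the impact of the proposed VR paradigm in women who suffered a gestational loss in the first 20 weeks of gestation", compared with usual follow-up; it names no outcome. The Data collection procedure section describes "a set of instruments that aim to assess symptoms of grief, depressive and anxious, and post-traumatic stress". Data collection tools then lists PGS, PCL-5 and HADS side by side, with HADS covering both anxiety and depression.

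Data processing and analysis lists the tests by type of variable and adds "For all statistical comparisons, a significance level of 5" per cent. Nowhere does the protocol name a primary outcome, an order of outcomes, an adjustment for multiple tests, or a statement of what result would support the hypothesis.

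**The concern.** A hypothesis worded in terms of significance needs a rule that turns the test results into a verdict. With four domains and none ranked, at least three rules fit the text:

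- any one significant scale supports the hypothesis;
- all four must be significant;
- each scale is reported on its own, with no overall verdict.

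The first two differ greatly in false-positive rate and in power. They give opposite answers whenever one, two or three scales are significant in favour of VR, which is a likely pattern if VR works. As written, the rule can be picked after the results are known.

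**Working it through.** The protocol gives no power, effect size or standard deviation, so there is no planned figure to reproduce.

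**Inputs from the protocol:** 20 women in two randomised groups (Sample and recruitment; Study design); four domains (AViR Project); Student's t-test, with Mann-Whitney for nonparametric variables, and a 5% level (Data processing and analysis).

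**Assumptions, not in the protocol:** 10 per arm; HADS anxiety and depression scored separately, giving four scores; two-sided tests, so 2.5% in the direction favouring VR; normal outcomes with equal correlation of 0 to 0.7 between scores, and 0.9 as an extreme.

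**Step 1. Any one scale suffices, no true effect.** For independent scales:

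- favouring VR: 1 − 0.975^4 = 9.6%;
- either direction: 1 − 0.95^4 = 18.5%;
- favouring VR, with HADS as one total (three tests): 1 − 0.975^3 = 7.3%.

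**Step 2. Effect that gives 80% power on one scale.** For a t-test with 18 degrees of freedom and noncentrality d × √(10/2), 80% power needs d = 1.325 SD. At d = 1.0 power is 56%; at d = 0.8 it is 39%.

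**Step 3. All four required.** For independent scales, joint power is the single-scale power to the fourth power: 0.80^4 = 41% at 1.325 SD; 0.562^4 = 10% at 1.0 SD; 0.395^4 = 2.4% at 0.8 SD.

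**Step 4. Correlated scales,** by simulation (400,000 trials per setting):

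| Correlation | 0 | 0.3 | 0.5 | 0.7 | 0.9 |
|---|---|---|---|---|---|
| No effect: at least one favours VR | 9.7% | 8.8% | 7.9% | 6.7% | 4.8% |
| No effect: at least one, either direction | 18.6% | 17.6% | 15.8% | 13.4% | 9.6% |
| 1.325 SD: all four favour VR | 40.8% | 49.1% | 54.8% | 61.1% | 69.5% |
| 1.325 SD: at least one favours VR | 99.8% | 98.7% | 97.0% | 94.1% | 88.7% |
| 1.325 SD: one to three (difference of the two rows above) | 59% | 50% | 42% | 33% | 19% |

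At smaller effects (200,000 trials), for correlation 0, 0.5 and 0.7:

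- 1.0 SD: joint power 10%, 25% and 32%.
- 0.8 SD: joint power 2.4%, 11.8% and 17.6%; at least one significant 86.6%, 71.0% and 63.4%; so one to three significant in 84%, 59% and 46%.

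**Step 5. Error under the all-four rule.** Success requires every test to favour VR significantly. If even one scale has no true benefit, the chance of success cannot exceed that scale's own 2.5%. It approaches 2.5% when the other three improve strongly. With no effect on any scale it is far smaller: 0.3% at correlation 0.7 and 0.9% at 0.9.

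**The case against.** Four objections deserve an answer.

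- **It is a feasibility pilot of 20 women, and usability and acceptance form the second objective.** This stands and lowers the weight. It does not remove the point. Study design says "To test the research hypothesis, the proposed study follows an experimental design", no efficacy test is called exploratory, and Dissemination of results aims to "inform end-users and health professionals of the benefits that a system such as the one proposed can have". That last sentence is an outreach aim, not a decision rule, but it shows what a positive reading would be used for.
- **The domains are joined by a plain conjunction, so all four are claimed and nothing is inflated.** This is the more literal reading. A reader might infer from the 7-10% that the trial as planned has that error rate. The documents do not support this, because the any-one rule is no more stated than the all-four rule. Separate reporting of each scale also fits a 5% level per comparison. The defect is that none of the three is chosen.
- **A statistical analysis plan may settle multiplicity.** It may settle the mechanics. The lead outcome, and what counts as support for a hypothesis stated in the protocol, belong beside that hypothesis.
- **The power figures depend on a chosen effect.** This stands. A reader might infer that 41-61% falls short of a planned 80%. The protocol plans no power; the 80% per scale is an assumption that requires 1.32 SD on every scale, and joint power is far lower at smaller effects.

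**Conclusion.** The point holds. The protocol sets a significance-based superiority hypothesis over four domains, ranks none, states no success rule and applies 5% to every comparison.

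Under the assumptions above (correlation 0-0.7), an any-one rule gives a 7-10% chance of a false result favouring VR, against 2.5% for one named outcome. An all-four rule never exceeds 2.5%, but its joint power is 41-61% at 1.32 SD and about 2-18% at 0.8 SD. The two readings disagree in 33-59% of trials at 1.32 SD.

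The absence of a rule is certain from the text. The sizes depend on the assumed arm size, effect and correlation, and on splitting HADS. Because this is a small feasibility pilot, the change is one that should be made rather than a fatal flaw.

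**What to change.** In the hypothesis paragraph (AViR Project) and in Data processing and analysis, before any post-intervention data are seen:

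1. **Name one primary efficacy comparison.** PGS total is suggested because the intervention is described as "specifically oriented to grief after an early gestational loss". The hypothesis itself ranks no domain, so the investigators should confirm the choice.
2. **Fix the test.** Compare groups on post-intervention PGS adjusted for baseline PGS (ANCOVA, two-sided 5%), added to the listed tests, with a stated rank-based fallback if residuals are clearly non-normal.
3. **State the rule.** The superiority hypothesis is supported only if this test is significant and favours VR.
4. **Make PCL-5, HADS-anxiety and HADS-depression secondary,** reported as group differences with 95% confidence intervals.
5. **Report within-group changes descriptively,** and say plainly that the significant-reduction part of the hypothesis is then not a confirmatory claim. Label all other tests exploratory.

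Naming a single outcome is what cures the defect. The baseline adjustment is an added gain in most settings: at 1.325 SD and 10 per arm, simulated ANCOVA power is 77%, 81%, 88% and 97% for assumed baseline-to-post correlations of 0, 0.3, 0.5 and 0.7, against 80% for the unadjusted t-test. The false-favourable rate stays at about 2.5%.

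The cost is a few sentences and no extra data, since PGS is already collected at both time points. There are two downsides. An effect mainly on the other domains would not count as primary success. ANCOVA also loses a little power (about 77% against 80%) if baseline and post-intervention scores are uncorrelated.
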